6.6 Dose Modification

No dose modifications are allowed during the study.

6.7 Intervention After the End of the Study

There is no planned intervention following the end of the study.

7 DISCONTINUATION OF STUDY INTERVENTION AND PARTICIPANT DISCONTINUATION/WITHDRAWAL

7.1 Discontinuation of Study Intervention

It may be necessary for a participant to permanently discontinue (definitive discontinuation) study intervention. If study intervention is permanently discontinued, the participant should remain in the study, ie, continue to participate in scheduled study visits and evaluations.

Note that discontinuation from study intervention is NOT the same thing as a withdrawal from the study. For procedures in the case of withdrawal from the study, see Section 7.2.

At each visit, participants will be instructed to contact the investigator immediately, if rash or skin reaction has developed. If maculopapular rash grade 1, 2, or 3 has developed, participant must be permanently discontinued from the study intervention and AZ medical staff should be informed.

- Grade 1: Macules/papules covering < 10% Body Surface Area with or without symptoms (eg, pruritus, burning, tightness).

- Grade 2: Macules/papules covering 10 - 30% Body Surface Area, with or without symptoms (eg, pruritus, burning, tightness); limiting Instrumental ADL (refer to preparing meals, shopping for groceries or clothes, using the telephone, managing money, etc); rash covering > 30% Body Surface Area with or without mild symptoms.
- Grade 3: Macules/papules covering > 30% Body Surface Area, with moderate or severe symptoms; limiting Self-care ADL (refer to bathing, dressing and undressing, feeding self, using the toilet, taking medications, and not bedridden).

If the participant develops a rash or skin reaction that is not considered a maculopapular rash, but is a generalised rash/skin reaction or is considered to be an SAE, the participant must be permanently discontinued from the study intervention and AZ medical staff should be informed.

For further information and skin reaction evaluation guidance, see Appendix B 5.

Study participants also may be discontinued from study intervention in the following situations:

- Participant decision. The participant is at any time free to discontinue treatment, without prejudice to further treatment.
- Adverse Event or other safety reasons as judged by the Investigator and/or sponsor where continued treatment may put the participant at undue risk.
- Development of uncontrolled and clinical significant **CCI** as judged by the Investigator.
- Severe non-compliance with the CSP.
- Pregnancy

At the time of permanent discontinuation of study intervention, an Early Discontinuation visit should be conducted. See the SoA (See Section 1.3) for data to be collected at the time of intervention discontinuation and follow-up and for any further evaluations that need to be completed.

7.1.1 Temporary Discontinuation

Every attempt should be made to maintain participants on the study intervention during the course of the study. If the study intervention has been interrupted, it should be re-introduced as soon as, in the opinion of the Investigator, the participant is able to re-start study treatment. Note related to AEoSI skin reactions (including maculopapular rash): In the occurrence of maculopapular rash CTCAE Grade 1, 2, or 3, or any other generalised rash/skin reaction or serious rash/skin reaction, study intervention should be permanently discontinued. At each visit, participants will be instructed to stop the study intervention and contact the investigator immediately if rash or skin reaction has developed. After the participant has been seen by the study doctor or designee and the skin reaction is not considered a maculopapular rash CTCAE

Grade 1, 2, or 3, or any other generalised rash/skin reaction or serious rash/skin reaction, the study treatment can be restarted.

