7.1.2 Rechallenge

Participants who have temporarily discontinued study intervention can resume treatment as soon as, in the opinion of the Investigator, the participant is able to re-start study treatment and the participant wishes to resume. No minimum time period is necessary before treatment can resume.

If a participant develops maculopapular rash CTCAE Grades 1, 2, or 3 or any other generalised rash/skin reaction or serious rash/skin reaction, study intervention should be permanently discontinued.

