8.2.5 Skin Reactions, Including Maculopapular Rash

Skin reactions, including maculopapular rash, will be considered AEs of special interest in this study. To ensure that data are collected systematically, any skin reaction will be recorded on a special eCRF page. All skin reactions should be recorded in the eCRF as an AE or SAE. If the rash is considered maculopapular, it will be evaluated using CTCAE grades 1-3 for rash maculopapular; if not considered maculopapular, severity will be captured as

mild/moderate/severe, along with data element components generally used for CTCAE grading of other skin reactions, given that CTCAE grading is specific to the particular type of skin lesion. For all rashes, various aspects of the rash will be documented, including start/end date, morphology of lesions (maculopapular vs other morphologies), body surface area impacted, anatomical site(s), symptoms, signs, effect on participant (including ADL impacted), concomitant medications, medication administered, and specific rash diagnosis, if available. Photos (overview and detailed) should be taken.

Please refer to Appendix B 5 for further guidance in rash assessment and reporting.

At all visits, participants will be instructed to contact the investigator immediately if rash or skin reaction has developed at any time point during the study. Participants will be recommended to make an acceptable quality self-photo of skin affected with rash/skin reaction.

If any study participant develops a confirmed generalised maculopapular rash CTCAE grade 1-3, throat tightness or angioedema at any time during the study, the investigator should immediately stop the study drug and arrange for the participant to receive the appropriate medical treatment relevant to this situation.

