Participants who develop skin reactions, including rash, will be asked to return to the clinic for an additional visit that will include a full physical exam and collection of blood samples for safety, hsCRP, and PK. If a participant is discontinued from investigational product and proceeds to the EDV, an exploratory biomarker sample and blood and urine samples for exploratory metabolite analysis will also be collected. The mandatory genetic sample per Section 8.6.3 should also be collected at the EDV if not previously collected from the participant. It is suggested to start the treatment with a topical steroid and/or oral antihistamine. The treatment should be individualised per participant and based on PI discretion. Upon PI discretion, a clinical dermatologist can be consulted and a skin biopsy considered. The participant can be provided with a treatment for the skin rash, according to clinical management standard. Blood samples should be drawn prior to treatment, if possible, and without delaying treatment.

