- Only half the dose is taken because the study participant feels that he/she is feeling better when not taking the whole dose
- Someone who is not enrolled in the study intentionally takes the drug

B 5 Guide to skin reaction assessment

This Appendix describes the process to be followed to appropriately identify, assess and report cases of skin reactions. Skin reactions, including maculopapular rash, will be considered AEs of special interest in this study. To ensure that data are collected systematically, any skin reaction will be recorded on a special eCRF page. All skin reactions should be recorded and reported as AEs or SAEs.

If the rash is considered maculopapular, it will be evaluated using CTCAE grades 1-3 for rash maculopapular; if not considered maculopapular, severity will be captured as mild/moderate/severe, along with data element components generally used for CTCAE grading of other skin reactions, given that CTCAE grading is specific to the particular type of skin lesion. For all rashes, various aspects of the rash will be documented, including start/end date, morphology of lesions (maculopapular vs other morphologies), body surface area impacted, anatomical site(s), symptoms, signs, effect on participant (including ADL impacted), concomitant medications, medication administered, and specific rash diagnosis, if available.

If maculopapular rash Grade 1, 2, or 3 has developed, participant must be permanently discontinued from IP, and AZ medical staff should be informed.

If the participant develops a rash or skin reaction that is not considered a maculopapular rash, the participant must permanently discontinue if the rash/skin reaction is considered an SAE or is a generalised rash/skin reaction. AstraZeneca medical staff should be informed.

At all visits, participants will be instructed to contact the investigator immediately if rash has developed at any time point during the study. Participants will be recommended to make an acceptable quality self-photo of skin affected with rash.

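### The rash stopping instructions do not match: only Section 7.1.1 tells participants to stop study drug, and the immediate-stop trigger in Section 8.2.5 is narrower than the permanent-discontinuation rule

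*Protocol*

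**What the plan says.** Four places in the protocol tell participants what to do about a rash.

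- Section 7.1: "participants will be instructed to contact the investigator immediately, if rash or skin reaction has developed".
- Section 7.1.1: "participants will be instructed to stop the study intervention and contact the investigator immediately". Treatment may restart once the participant has been seen and the reaction found not to qualify for permanent discontinuation.
- Section 8.2.5: "participants will be instructed to contact the investigator immediately if rash or skin reaction has developed at any time point".
- Appendix B 5: "participants will be instructed to contact the investigator immediately if rash has developed".

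The rule for the investigator appears in five places. Section 7.1 states: "If maculopapular rash grade 1, 2, or 3 has developed, participant must be permanently discontinued from the study intervention". It adds any other rash or skin reaction that is generalised or an SAE. Sections 7.1.1 and 7.1.2 and Appendix B 5 have the same scope; Section 7.1.2, for example, applies to a participant who "develops maculopapular rash CTCAE Grades 1, 2, or 3 or any other generalised rash/skin reaction or serious rash/skin reaction". Section 8.2.5 differs. It tells the investigator to stop drug at once if a participant "develops a confirmed generalised maculopapular rash CTCAE grade 1-3", or has throat tightness or angioedema.

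Section 8.2.5 also says that participants with a skin reaction "will be asked to return to the clinic for an additional visit". It gives no time limit for that visit.

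**The concern.** Maculopapular rash is the first identified risk in Table 3 of the protocol. It has its own discontinuation criteria and special eCRF page, and dermatologists sit on the Part A and Part B safety committees. The instructions for this event should therefore read the same wherever a site looks, and they differ in two respects.

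First, whether a participant is told to stop dosing before being seen depends on which section the site uses. Section 4.3 places onset in healthy volunteers around 7 to 10 days after the first dose, and the first scheduled post-dose visit is Day 29 in both parts. The participant will normally be at home, dosing daily, and relying on what was said at randomisation.

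Second, a limited grade 1 maculopapular rash can be read as outside the Section 8.2.5 trigger although Section 7.1 requires permanent discontinuation. Grade 1 has already been reported at 5 mg, which is a Part A dose and a possible Part B dose.

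What is at stake is avoidable dosing between onset and review. No effect on power, type I error, dose selection, rash counts or trial results is claimed.

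**Working it through.** **Text comparison**

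| Place | Participant told to stop? | Rash for which the investigator must stop drug |
|---|---|---|
| 7.1 | No, contact only | Any maculopapular grade 1–3; other generalised or serious reaction |
| 7.1.1 | Yes, stop and contact | Same as 7.1 |
| 7.1.2 | No participant instruction | Same as 7.1 |
| 8.2.5 | No, contact only | Maculopapular grade 1–3, only if confirmed and generalised (plus throat tightness, angioedema) |
| Appendix B 5 | No, contact only | Same as 7.1 |

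One of the four participant instructions includes stopping. For rash, the Section 8.2.5 trigger leaves out three groups that the permanent rule covers:

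1. maculopapular rash that is not generalised;
2. generalised rash that is not maculopapular;
3. serious skin reactions that are not maculopapular.

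The requirement that a rash be generalised also sits badly with grade 1, defined as under 10% of body surface.

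**Cross-references.** Sections 7.1 and 8.2.5 both send the reader to Appendix B 5 for skin reactions. Appendix B 5 presents itself as the process to follow but contains no stop instruction for the participant. None of the three points to Section 7.1.1 for rash.

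**Time from onset to the first scheduled visit**

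Inputs: onset 7 to 10 days after a Day 1 dose (Section 4.3); visit on Day 29, with a window of ±3 days in Part A (Table 1) and ±7 days in Part B (Table 2).

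- Onset day: 1 + 7 = 8 to 1 + 10 = 11.
- Gap to Day 29: 29 − 11 = 18 to 29 − 8 = 21 days.
- Part A window (Day 26 to 32): 26 − 11 = 15 to 32 − 8 = 24 days.
- Part B window (Day 22 to 36): 22 − 11 = 11 to 36 − 8 = 28 days.

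These gaps are ceilings, because every version of the instruction asks for immediate contact. The documents give no time to review. With an assumed delay of 1 to 7 days and one dose a day, a participant who does not stop takes 1 to 7 further doses.

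**Expected rashes in the Part A 5 mg arm**

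Inputs: 1 of 27 at 5 mg in Phase 2a and 2 of 12 at 5 mg in the Japanese and Chinese study (Section 4.3); 220 randomised per arm (Section 1.1).

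- 1/27 = 3.7% (exact 95% CI 0.1% to 19.0%); × 220 = 8.1.
- 2/12 = 16.7% (exact 95% CI 2.1% to 48.4%); × 220 = 36.7.

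This gives about 8 to 37 participants with a maculopapular rash. It does not count participants who keep dosing because of the wording; that number is unknown.

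**The case against.** The strongest reply is that nothing is missing. Section 7.1.1 applies at each visit, including randomisation, so a site that gives contact-only advice is not following the protocol. Silence in the other sections does not contradict it. The Section 8.2.5 sentence is not worded as an exclusive trigger. It pairs rash with throat tightness and angioedema and goes on to treatment, so it can be read as acute management, and in those two terms it is broader than Section 7.1. An investigator who sees a limited grade 1 rash still meets an unambiguous requirement to discontinue in Section 7.1 and Appendix B 5. Section 8 also asks that immediate safety concerns be discussed with the sponsor at once.

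The figures are open to challenge too. The review delay is assumed. The 7 to 10 day onset was seen at 15 mg and above, while the one Phase 2a case came 5 days after up-titration to 5 mg. The upper figure applies a rate from Japanese and Chinese volunteers to a whole arm, although most countries in SAP Section 4.1.3 are outside Asia. Section 4.3 does not say whether the grade 1 case was localised. Consent material is not available for this review, so what participants are actually told cannot be judged.

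Most of this stands. The sections can be followed together, the permanent rule is the same in four places, and the counts are illustrative. What remains is a stated safety trigger whose scope for rash is too narrow, and cross-references that lead to a procedure without the stop instruction. The one complete instruction sits under Temporary Discontinuation, in a section that opens by urging sites to keep participants on treatment.

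**Conclusion.** The concern holds. One of four participant instructions says to stop study drug, and the Section 8.2.5 immediate-stop trigger omits three groups of rash that must lead to permanent discontinuation elsewhere. The text comparison is certain.

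The consequence is less certain. It is limited to doses taken between onset and review by participants or sites using the contact-only or narrower wording: 1 to 7 doses each under the assumed delay, in some unknown fraction, possibly none, of the 8 to 37 participants projected to have a rash. This is a patient-safety wording fault that should be corrected because it concerns the main identified risk and is cheap to put right.

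**What to change.** Use the Section 7.1.1 instruction in Sections 7.1 and 8.2.5 and in Appendix B 5: on any rash or skin reaction, stop study drug and contact the investigator immediately; restart only after review shows that it is neither a maculopapular rash of CTCAE grade 1 to 3 nor another generalised or serious skin reaction.

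In Section 8.2.5, drop the qualifiers confirmed and generalised from maculopapular rash. The immediate-stop trigger then becomes any maculopapular rash of CTCAE grade 1 to 3, any other generalised or serious rash or skin reaction, throat tightness, or angioedema.

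The cost is wording changes in three places and some short dose interruptions for rashes that turn out not to qualify. Section 7.1.1 already accepts those by allowing restart after review, and Section 7.1.2 requires no minimum wait. Neither change creates a new policy: both reuse rules already in the protocol.

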7.1.2 Rechallenge

Participants who have temporarily discontinued study intervention can resume treatment as soon as, in the opinion of the Investigator, the participant is able to re-start study treatment and the participant wishes to resume. No minimum time period is necessary before treatment can resume.

If a participant develops maculopapular rash CTCAE Grades 1, 2, or 3 or any other generalised rash/skin reaction or serious rash/skin reaction, study intervention should be permanently discontinued.

7.2 Participant Withdrawal from the Study

A participant may withdraw from the study (eg, withdraw consent) at any time (study intervention and assessments) at his/her own request, without prejudice to further treatment, or may be withdrawn at any time at the discretion of the investigator for behavioural, compliance, or administrative reasons. This is expected to be uncommon.

A participant who considers withdrawing from the study must be informed by the investigator about modified follow-up options (eg, telephone contact, a contact with a relative or treating physician, or information from medical records).

At the time of withdrawal from the study, if possible, an EDV should be conducted, as shown in the SoA (See Section 1.3). If the participant is discontinued from study intervention, and later decides to withdraw from the study before scheduled EoS visit, the EoS visit should be performed at the time of withdrawal. See the SoA (See Section 1.3) for data to be collected at the EDV and EoS visit. For procedures in the case of discontinuation from study intervention, see Section 7.1.

If the participant withdraws consent for disclosure of future information, the sponsor may retain and continue to use any data collected before such a withdrawal of consent.

If a participant withdraws from the study, it should be confirmed if he/she still agrees for existing samples to be used in line with the original consent. If he/she requests withdrawal of consent for use of samples, destruction of any samples taken and not tested should be carried out in line with what was stated in the informed consent and local regulation. The investigator must document the decision on use of existing samples in the site study records and inform the Global Study Team.

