^d EoS visit will take place 4 weeks after final dose, which may occur after 24, 36 or 48 weeks of treatment. For participants who are discontinued from the study intervention, and later decide to withdraw from the study before scheduled EoS visit, the EoS visit should be performed at the time of withdrawal.

^e V6 will occur only for participants treated for at least 36 weeks.

^f V7 will occur only for participants treated for 48 weeks.

^g To avoid bias in participant responses, KCCQ will be completed prior to any other study procedures, following informed consent.

^h At Visits 1 and EoS/EDV, a full physical examination is performed.

- i Vital Signs: supine BP (average of 3 measurements), pulse rate, and body temperature will be measured.
- j An additional, local NT-proBNP test can be performed as pre-screening at the site. Participants must sign the specific Pre-Screening Informed Consent before collection of a blood sample for this procedure. This test can be done within 30 days preceding the Screening (Visit 1), and latest on the day of the Screening (Visit 1). The central lab result will be used to determine if the participant is eligible for the study.
- k **CCI** [REDACTED]
- l Screening echocardiogram can be performed on a different day if it is not possible to be done on the screening visit day due to scheduling purposes but must be performed as soon after the screening visit as possible in order to allow for results to be available prior to randomisation. Screening echocardiogram is not needed if there is an available echocardiogram performed up to 12 months before screening.
- m To be sampled at Visit 2 and either Visit 5, Visit 6 or Visit 7, for participants treated for either 24, 36 or 48 weeks, respectively.
- n The first dose of study intervention will be administered in clinic on the day of randomisation after completing all pre-dose procedures. Participants will receive study intervention at the site on visit days and at home between visits for a total of 24, 36 or 48 weeks
- o AEs will be collected from the first dose. SAEs will be collected from signing of the ICF

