Intercurrent events: Patients with intercurrent events resulting in missing assessments of the primary endpoints, eg, terminal events or withdrawal from the study, is expected to be very few and will be excluded from the analysis (principal stratum strategy). Other intercurrent

events, eg, premature discontinuation of study treatment, will be ignored (treatment policy strategy).

Population-level summary: Difference in adjusted mean change from baseline between groups.

Missing data will not be imputed.

Part B:

Treatment: Treatment with either 2.5 mg or 5 mg AZD4831 compared to placebo, administered in addition to optimal back-ground therapy for co-morbidities.

Population: Patients that fulfill all of the inclusion and none of the exclusion criteria.

Endpoint: Change from baseline to 24 weeks in KCCQ-TSS and 6MWD.

Intercurrent events:

- Deaths will be handled by a While-alive strategy, implemented by using the change from baseline to 24 weeks or last measurement prior to death (if earlier than 24 weeks).
- Intercurrent events other than deaths will be handled by a Treatment-policy strategy, ie, measurements will be collected and used in the statistical analysis regardless of the occurrence of the event

Population-level summary: Between group difference in mean change from baseline at 24 weeks or prior to death, if earlier. For KCCQ-TSS, this will be a function of baseline values.

For patients with missing measurements for reasons other than death, a multiple imputation scheme will be employed, which differentiates between monotonous and non-monotonous missing data. Monotonous missing data are where observations are consistently missing after a point in time whereas non-monotonous missing data are missing observations followed by at least one recorded observation. For monotonous missing data, retrieved dropouts (patients remaining in the study despite same intercurrent events as drop-outs) will be used to impute missing values or, if there are too few retrieved dropouts, a Jump-to-reference approach utilizing placebo patients will be applied.

As a supplementary approach, analyses where deaths are combined with the outcome variables in a Composite strategy will be conducted, and will be described in the SAP for Part B.

Methods for multiplicity control, both Part A and Part B:

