- Death: With the exception of assessment of mortality, will be handled hypothetically as it cannot occur, implemented by censoring time to event data at death and not imputing any data after death.

Population level summaries: Distribution of endpoints by treatment group, Kaplan-Meier estimate for endpoints by treatment group, difference in Kaplan-Meier estimates between treatment groups and treatment hazard ratios.

This estimand requires that to the extent possible, randomised subjects are followed up regardless of study intervention compliance and adherence to the study protocol.

Adverse Events

All AEs will be classified by system organ class, high level group term, high level term, and preferred term according to MedDRA.

AEs will be presented for each treatment group by SOC and/or PT, covering number and percentage of subjects reporting at least one event. An overview of AEs will present for each treatment group the number and percentage of subjects with any AE, AEs with outcome of death, serious AEs, and AEs leading to discontinuation of IP. Separate AE tables will be provided taking into consideration seriousness, death, and events leading to discontinuation of IP. An additional table will present number and percentage of subjects with most common AEs. Most common (eg, frequency of $>x\%$, $\geq x\%$) will be defined in the SAP. In accordance with the requirements of the FDA, a separate table will present non-serious AEs occurring in more than 5% of subjects in any treatment group. Key subject information will be presented for subjects with AEs with outcome of death, serious AEs, and AEs leading to discontinuation of IP. An AE listing for the safety analysis set will cover details for each individual AE. AEoSIs related to skin reactions, including maculopapular rash, and infection will be presented. Full details of AE analyses will be provided in the SAP.

All safety analyses are descriptive; hence no p-values will be presented for any safety analyses, and confidence intervals are provided as an illustration of precision of the estimate. Hazard ratio between treatment groups will be based on a Cox proportional hazards regression model with a factor for treatment group.

Treatment emergent

For Part A, the definition for treatment emergent events will be provided in the SAP.

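### A participant already off study drug who then withdraws is sent to an EoS visit with no KCCQ or 6MWT, so an obtainable off-treatment value of the primary endpoints is not collected

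*Protocol*

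**What the plan says.** Section 7.2 of the protocol gives two instructions for a participant who leaves the study. The general one is: "At the time of withdrawal from the study, if possible, an EDV should be conducted, as shown in the SoA". The second covers a participant who has already stopped study drug and "later decides to withdraw from the study before scheduled EoS visit, the EoS visit should be performed at the time of withdrawal". Footnote d to Table 2 (Part B Schedule of Activities) repeats this for Part B: "the EoS visit should be performed at the time of withdrawal".

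In Table 2 the EDV column is marked for KCCQ, PGIS-HF and PGIS-WD. The EoS column is blank for all three and for 6MWT. In Part A, Table 1 marks KCCQ at Visit 11/EDV but not at Visit 12, and Figure 1 shows no efficacy measurement at follow-up.

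For Part B, Section 9.4.2.1 handles intercurrent events other than death by treatment policy: "measurements will be collected and used in the statistical analysis regardless of the occurrence of the event". Values missing for other reasons are multiply imputed, using retrieved dropouts for monotone gaps, or jump-to-reference if there are too few of them. For Part A, the same section and SAP Section 4.2 exclude participants without the assessment and do not impute.

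Section 7.2 also says a participant "may be withdrawn at any time at the discretion of the investigator for behavioural, compliance, or administrative reasons. This is expected to be uncommon". Section 9.4.3, under the safety estimand and as far as is possible, asks that "randomised subjects are followed up regardless of study intervention compliance and adherence to the study protocol".

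**The concern.** A treatment-policy estimand depends on outcomes measured after study drug is stopped. Under Section 7.2, a participant who stops drug and leaves at the same time has an EDV with KCCQ. One who stopped earlier, stayed in follow-up and then leaves has a face-to-face visit with neither primary endpoint. The second participant is the one whose current state is off-treatment, so the plan gives up an off-drug value at a visit that takes place anyway.

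At stake is a modest amount of information. In Part A it can decide whether a participant enters the primary analysis at all. In Part B it affects how far the analysis leans on imputation.

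The compliance ground for investigator withdrawal is a secondary matter. Section 7.1 lists severe non-compliance with the protocol as a possible reason to stop study drug and says that stopping drug is not withdrawal. Section 7.2 lets compliance reasons end participation, assessments included.

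**Working it through.** **1. What each final visit collects**

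| Visit | KCCQ | PGIS-HF, PGIS-WD | 6MWT |
|---|---|---|---|
| Part B EDV | marked | marked | blank in Table 2, listed in Figure 2 |
| Part B EoS | blank | blank | blank |
| Part A Visit 11/EDV | marked | not readable (redacted) | listed in Figure 1 |
| Part A Visit 12 | blank | not readable (redacted) | none in Figure 1 |

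Section 7.2 does not define the EoS visit for Part A. I read it as Visit 12, which the synopsis describes as the end of study visit.

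**2. Who is affected**

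- Stops drug and stays: attends the scheduled visits (Sections 4.4 and 7.1), with KCCQ and 6MWT in Part B at Weeks 16, 24, 36 and 48. No loss.
- Withdraws after the primary visit: no loss to the primary analysis.
- Stops drug, stays, then withdraws before the primary visit and attends a final visit: the gap applies.

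**3. What a value at withdrawal could do**

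Part A: SAP Sections 3.3.2 and 3.3.3 assign to Week 16 the assessment closest to Day 113 within Days 100 to 141, scheduled or not. A withdrawal visit in Week 15 (Day 106) would therefore supply a Week 16 value if KCCQ and 6MWT were done. Before Day 100 it would not, and the participant would still be excluded.

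Part B: Week 24 is Day 169 ± 7, that is Days 162 to 176, as a visit window. Withdrawal at Week 22 is about Day 22 × 7 + 1 = 155, outside it. Whether that value could count as Week 24 or would only inform the imputation depends on analysis windows in the Part B SAP, which I do not have.

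**4. Size, tested on power**

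The check uses Part B 6MWD, the endpoint with less stated power (95%, against more than 99% for KCCQ-TSS). Inputs from Section 9.2 and the synopsis: difference δ = 19 m, SD σ = 70 m, two-sided α = 0.025, 820 randomised 1:1, so n = 410 per arm.

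Power = Φ(δ / (σ√(2/n)) − z), with z = 2.241.

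- Plan's figure: σ√(2/410) = 4.889 m; 19/4.889 − 2.241 = 1.645; power 95.0%. Critical value 2.241 × 4.889 = 10.96 m. Both reproduce the stated 95% and 11 m, so the plan counts all 820.
- With 745 (372.5 per arm): standard error 5.129 m, power 92.8%, critical value 11.5 m.

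The documents give no rate for this pattern of departure, so the share w without a Week 24 value is an assumption. The diluted column keeps 410 per arm and shrinks the effect to 19 × (1 − w), as if jump-to-reference removed the effect in those participants.

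| w (assumed) | Participants of 820 | Complete cases | Diluted effect |
|---|---|---|---|
| 2% | 16 | 94.6% | 94.1% |
| 5% | 41 | 93.9% | 92.7% |
| 9.1% | 75 | 92.8% | 90.1% |
| 15% | 123 | 91.0% | 85.6% |

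The 9.1% row is all 75 participants without complete safety data (820 − 745). The affected group can be only part of any such loss. The 15% row exceeds the plan's own allowance and is there to show the range.

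In Part A, the 6MWD figures of 21 m and 14 m reproduce at 200 per arm (20.97 m and 13.7 m), so that calculation already uses 600 of the 660 randomised.

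**The case against.** The strongest reply is that the plan already protects off-treatment data and the gap is marginal. Participants who stop drug are to stay in the study and attend scheduled visits, and a KCCQ is taken at the EDV when drug stops. Section 7.2 expects withdrawal to be uncommon and adds: "A participant who considers withdrawing from the study must be informed by the investigator about modified follow-up options". A measurement at withdrawal will often fall outside the analysis window. All of this stands and limits the size of the point. It does not close the gap: the modified options named are contacts and records, not KCCQ or 6MWT, and the EDV value dates from when drug was stopped.

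Four stronger readings are tempting but unsupported.

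- **These participants are the retrieved-dropout donors.** Section 9.4.2.1 defines retrieved dropouts as people who remain in the study. Someone who withdraws before Week 24 receives imputation and is not a donor.
- **Observed values are thrown away.** Data collected before withdrawal are kept and used. What is forgone is one further value.
- **Loss will differ by arm because of rash.** Rash leads to stopping drug, not to leaving the study. No document links it to later withdrawal.
- **A share of the 75 gives the number affected.** Complete safety data is not defined, and the 75 may include deaths, people lost with no final visit, and departures after Week 24. The documents support no particular share.

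On compliance, the follow-up sentence in Section 9.4.3 belongs to the safety estimand and is qualified, and the Section 7.2 power is discretionary. That makes it a wording conflict of unknown and probably small effect.

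**Conclusion.** The point holds as a narrow gap in data collection. Section 7.2 and Table 2 footnote d provide a final visit without either primary endpoint for participants who stopped drug earlier and then withdraw. That sits badly with the stated intention to collect measurements whatever intercurrent event occurs. In Part A, the missing value excludes a participant whose withdrawal visit falls on Days 100 to 141 and who has no other value in that window. In Part B, the imputation works with less information.

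The number affected is not in the documents and should be small. Stated power of more than 90% is not threatened: 6MWD power stays at 90.1% or higher for assumed losses up to 9.1%, a ceiling well beyond this group's likely size. The conclusion assumes that the Part A EoS visit is Visit 12 and that the Part B imputation can use an off-schedule value. It is worth correcting because correction is cheap.

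**What to change.** 1. In Section 7.2 and Table 2 footnote d, state that when the EoS visit is held early because of withdrawal, KCCQ, PGIS-HF, PGIS-WD and, where the participant is able, 6MWT are done as well as the EoS items, with the questionnaires first as the protocol already requires. Make the same change for Part A Visit 12, with the PGIS items only if that part collects them. An EoS visit held on schedule is unchanged.
2. Reconcile Table 2, where 6MWT is blank at the EDV, with Figure 2, which lists it there. Until then, holding an EDV in place of the EoS visit would not secure 6MWD.
3. Reconcile the compliance ground for investigator withdrawal in Section 7.2 with Sections 7.1 and 9.4.3, so that non-compliance with study drug does not by itself end follow-up. The grounds for stopping drug need not change.

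Cost: a sentence in Section 7.2, a footnote, a visit activation on the questionnaire tablet, and two consistency edits. The participant has a few minutes of questionnaires and, if able, a walk test at a visit that already takes place. The downside is that slight extra burden on someone who is leaving.
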